2.0 CHAPTER TWO: Problem statement, justification, and conceptual framework

2.1 Problem statement

Neonatal outcomes are highly correlated with the health of the mother, an example of this is shown repeatedly by poor rates of survival of infants after maternal death^{1,2}. Prediction of risk, based on the mother and infant as a pair, is a major gap in current research and yet vital to the survival of both the mom and the infant. In our prior epidemiological study of post-discharge outcomes among 3,236 dyads, we found that most readmissions were due to infectious illness and occurred early in the post-discharge period. Of the 2,926 dyads with complete follow-up data 7.1% of dyads reported at least 1 outcome. 3.6% of newborns were readmitted, 0.8% died, and 2.7% of mothers were readmitted. For readmitted newborns, the most common diagnosis was sepsis (63%), and 19% were in respiratory distress at readmission. For readmitted mothers, the most common diagnoses were surgical site infections (51%), puerperal sepsis (43%), malaria (19%), and other infections (5%). Considering the health of the mother and newborn as a dyad is an innovative and effective approach as the health of a child is closely linked to the health of its mother. A mother's morbidity or mortality affects the health of all her children – and newborns whose mothers died during the first 6 weeks have an even greater risk of dying than those whose mothers survive¹⁵. Thus, we can improve maternal and child health outcomes by identifying both mothers and babies at increased risk of mortality or serious morbidity after hospital discharge and allocating scarce resources for targeted follow-up to those most vulnerable. This allows us to not only improve health outcomes but benefits the health system with efficient use of resources.

[figure not shown]

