4.6.3 Study Procedures

Phase I: Observational Cohort Study

I. Admission

- a. The study team will collect admission variables and health and pregnancy history through chart review and interviews with the participant. Data will not be collected during periods of maternal stress. In this case, incomplete interview questions will be deferred to the discharge interview.
 1. Admission variables: These questions include mode of transport, maternal demographic and socioeconomic variables (e.g., distance travelled to the hospital, age, location of residence). Data collected will also include vital signs (e.g., temperature, blood pressure, heart rate).
 2. Health and pregnancy history: This includes questions on number of previous pregnancies, comorbidities, prior admissions, and medication history.

II. Delivery

- a. Maternal variables: The study team will collect data related to the delivery including mode of delivery, method of induction, noted vaginal or perineal tearing, and any other major events or conditions occurring during delivery.
- b. Neonatal variables: Data will be collected related to the delivery including sex, Apgar score, weight, and resuscitation with oxygen therapy at birth.

III. Discharge

- a. Clinical Data Collection: A maternal and neonatal clinical examination will occur prior to discharge.
 1. Maternal Clinical Exam: Research nurses will record clinical signs and symptoms including SpO₂, heart rate, blood pressure, respiratory rate, and body temperature. We will also collect a small sample of blood (200 microlitres) to test hematocrit levels.
 2. Neonatal Clinical Exam: Research nurses will record clinical signs and symptoms data including weight, SpO₂, body temperature, and urination and defecation status. Data will also be collected on the infant's health status prior to discharge including NICU admission.
- b. Patient Interview: Following delivery, and prior to discharge, research nurses will conduct a structured interview and collect data including breastfeeding status, any symptoms experienced (e.g., headache, chest pain, difficulty emptying bladder, etc.).

IV. 6 Week Maternal and Newborn Follow-up (Outcomes)

- a. Telephone Interview: Research nurses and field officers will follow-up all dyads at 6 weeks postpartum to collect data on post-discharge care seeking and health outcomes, as well as newborn care practices. A verbal autopsy will be performed in all cases of newborn or maternal death. If

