the mother or newborn was readmitted or died, data on clinical signs and symptoms and diagnoses during readmission or at death will be collected.

Phase II: Journey Mapping

- I. Journey mapping: We will ask a randomly selected group of mother-infant dyads (n=100) additional questions to ascertain their movement through the hospital, perspectives on the current system of post-natal care, and post-discharge pathways, at various time periods including in the postnatal patient interview, 72 hour post-discharge follow-up, and at the 6 week follow-up telephone interview.

Phase III: Process Mapping

- II. We will establish one working group (n=8) per facility who will be engaged in a process mapping exercise which is a qualitative methodology commonly used in quality improvement interventions. Process mapping exercises will be facilitated by a research assistant to gain an understanding of the post-natal discharge process as it currently operates and to identify inefficiencies to care and potential solutions. Working groups will engage in a brainstorming session using paper, pens, and sticky notes to map out the discharge pathways of their respective facilities. Group members will work together to identify all stages of the process and indicate the individuals involved at each stage. When the working group reaches consensus and deems the flowchart complete and accurate, it will then be analyzed by members to identify problems, bottlenecks, and non-value-added steps such as unnecessary work, duplication, or communication breakdowns. After process inefficiencies are identified, teams will brainstorm, first individually then as a group, to identify potential solutions. The process mapping exercise will take 90-120 minutes per facility. The facilitator will use prompts to motivate participants to discuss topics in greater detail as needed. All process data will be mapped to a stage of the discharge process to provide a comprehensive model of post-natal discharge processes from the provider perspective.

Phase IV: Focus Group Discussion

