4.8 Outcomes (Phase I)

The primary outcome is maternal and/or neonatal death or need for re-admission within six weeks of birth.

Secondary outcomes include:

1. Post-natal care visits during the 6-week post-discharge period
2. post-discharge health seeking practices for mothers/newborns during the 6-week post-discharge period
3. Causes of readmission/mortality among those who experience such outcomes, based on verbal autopsies and admission symptom/diagnosis questionnaires

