		Number of people in household
		Number of children in household including baby
		Marital status
		Do you live with the father of the baby
		Maternal level of education (no school, P4-7, S1-6, post-secondary)
		SES Index (score out of 8), includes the following questions
		
 a. Finished floor material b. flush toilet c. LPG/electricity for cooking fuel d. improved source of drinking water (with defn) e. more than one room in home f. electricity g. television h. refrigerator i. smart phone j. car, motorbike, bicycle, truck
		Have any other of your children died – Y/N
72-hour post-discharge	Maternal and Newborn Follow-up Telephone Interview	Travel time from hospital to home
		Mode of transport from hospital to home
		Did the time of discharge affect trip home?
		Barriers encountered on journey home
		Patient experience measures (Likert scales – e.g., felt healthcare worker spent enough time preparing them for discharge, were things explained in a way that was easy to understand, quality of discharge experience, etc.)
6 weeks post-discharge	Maternal Variables – Follow-up Interview	Is the mother alive
		Did she seek care at any time after being home post delivery
		How many routine postpartum visits were made after discharge following birth
		Number of days after birth first PNC visit was made
		Admitted for one or more nights for any reason after being home with her baby post-delivery
		During admission any of the following (vaginal bleeding, abnormal tiredness, convulsions, shortness of breath, vision changes, severe headaches, abdominal pain, abdominal tenderness, foul smelling

	vaginal discharge, fever/body hotness, diarrhea, vomiting everything, cough, loss of consciousness, other)
	Diagnosis (was she told she had pre-eclampsia, eclampsia, HIV, malaria, heavy bleeding, surgical site infection, puerperal sepsis, other infection, diarrhea, vomiting, PPD/psychosis, other)
	Admission date
	Number of nights she was in hospital due to these conditions
	Was hospital care sought prior to her death?
	Was the care sought for routine postpartum follow-up?
	How many routine postpartum visits were made after discharge following birth?
	How many days after birth was the first PNC visit made?
	Did mom get sick during first 6 weeks (Y/N)
	If yes, did she seek care (Y/N)
	If yes, was she re-admitted (Y/N – also how many times and when)
	During this illness, did she experience any of the following symptoms

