	Are you based in the same home that you were in prior to delivery
	Support present during post-partum period (list: ex. mother, mother-in-law, etc.)
	Verbal autopsy for mothers who die
6-week post-discharge	Neonatal Variables – Follow-up interview
	Is the newborn alive at the time of the follow up interview
	Did the newborn die without ever having been discharged following birth
	Date of death
	Place of death
	Was hospital care sought prior to their death
	How many PNC check-ups were completed after leaving the hospital following birth
	How many days old was his baby when the first PNC check was done after leaving the hospital following birth
	Was the newborn admitted for one or more nights at a facility for any reason after being home post-delivery?
	Number of days from discharge till readmission
	Symptoms during illness (rash, cough, diarrhea, fever/hotness of body, vomiting everything, abnormally sleepy, changes in urine colour, making less urine than usual, blood in stool, seizure/convulsions, yellow soles, feeding status, no symptoms, don't know)
	Baby's feeding/drinking status currently

	For how many weeks after delivery was the child exclusively breastfed?
	Is child being exclusively or Non-exclusively breastfed
	For neonates who were readmitted were you told the child had (sepsis, respiratory distress, endocrine/metabolic disease, trauma/injury)
	Are they still in hospital due to this/these conditions
	How many nights were they in hospital due to this/these conditions?
	Did you seek care for the newborn at a facility at any time after being home post-delivery?
	Was this care for routine vaccinations or postnatal baby check-ups?
	How many postnatal baby check ups were completed after leaving hospital following birth?
	How many days old was this baby when the first postnatal check was done after leaving hospital following birth?
	For children who died: Verbal autopsy
	Timing of PNC visits: time from discharge to PNC visit and subsequent visits

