Appendix D: Neonate Outcomes

Table 8. Neonatal Outcomes (n=134)

Readmission n=108	n (%)
Diagnosis	
Sepsis	68 (63.0%)
Respiratory distress	21 (19.4%)
Endocrine/Metabolic Disease	2 (1.9%)
Trauma/Injury	2 (1.9%)
Deaths n=26	
Period from delivery to death (days) median [interquartile range]	5.00 [3.00-14.8]
Period from discharge to death (days) median [interquartile range]	4.00 [1.25-13.8]
Location of death n (%)	
Home	9 (34.6%)
Hospital	13 (50.0%)

En route to hospital	4 (15.4%)
Was hospital care sought prior to death n (%)	
Yes	16 (61.5%)
No	10 (43.5%)
Symptoms (n=131)	
Fever/hotness of body < 7 days	72 (55.0%)
Cough < 14 days	7 (5.3%)
Fever/hotness of body > 7 days	5 (3.8%)
Abnormal sleeping	5 (3.8%)
Changes in urine color	4 (3.1%)
Seizure/Convulsions	4 (3.1%)
Diarrhea < 14 days	3 (2.3%)
Rash	12 (9.2%)
Vomiting	10 (7.6%)
Yellow Soles	10 (7.6%)
None of these symptoms	10 (7.6%)
Cough > 14 days	1 (0.8%)
Diarrhea > 14 days	1 (0.8%)
Less urine than usual	1 (0.8%)
Blood in stool	1 (0.8%)
Unknown	1 (0.8%)

Table 9. Neonatal Care Seeking

Care Seeking n = 131 (108 readmitted+23 dead)	
Did you seek care for the newborn at a facility after being home post delivery n (%)	
Yes	108 (82.4%)
No	0 (0%)
Missing	23 (17.6%)
How many post natal baby check ups were completed after leaving hospital following birth	
0	3 (2.3%)
1	1 (0.8%)
2	33 (25.2%)
≥3	50 (38.2%)
Missing	44 (33.6%)

How many days old was this baby when the first post natal check was done after leaving hospital following birth median [interquartile range]	8.00 [3.75-21.0]
Number of days from discharge to readmission median [interquartile range]	2.00 [0-8.00]

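### The newborn readmission diagnosis item has no 'other' or 'not told/don't know' option, so secondary outcome 3 would be only partly answered for newborns

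*Combined protocol and SAP*

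**What the plan says.** Section 4.8 makes the cause of readmission or death a secondary outcome: "Causes of readmission/mortality among those who experience such outcomes, based on verbal autopsies and admission symptom/diagnosis questionnaires". Section 4.6.3 describes the sources. For deaths, "A verbal autopsy will be performed in all cases of newborn or maternal death". For a mother or newborn who was readmitted or died, "data on clinical signs and symptoms and diagnoses during readmission or at death will be collected".

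Appendix A (Variables Collected, 6-week neonatal follow-up) gives the newborn diagnosis item as "For neonates who were readmitted were you told the child had (sepsis, respiratory distress, endocrine/metabolic disease, trauma/injury"). These four conditions are the whole list. The newborn symptom item in the same block ends "yellow soles, feeding status, no symptoms, don't know"), so it has a 'don't know' but no 'other'.

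The maternal diagnosis item in the same appendix has twelve options and ends "surgical site infection, puerperal sepsis, other infection, diarrhea, vomiting, PPD/psychosis, other").

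Appendix D, Table 8, reports the prior cohort's newborn readmissions under the heading "Readmission n=108". It uses the same four diagnoses and has no 'other' or 'missing' row.

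**The concern.** A cause-of-readmission outcome needs every readmission to end in a category, even if that category is 'other' or 'unknown'. As Appendix A is written, a readmitted newborn whose family was told of some other condition, or was told nothing, would have no answer to record. In the data, three situations would look alike: another diagnosis, no diagnosis conveyed, and a missing response.

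This is more than a formal worry, because the prior cohort reported with these four categories already shows an unexplained remainder. Verbal autopsy is planned for deaths. For readmitted newborns who survive, the cause therefore rests on this item and the symptom list. What is at stake is how complete and interpretable the newborn part of secondary outcome 3 will be.

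**Working it through.** **Inputs.** From Appendix D, Table 8: 108 newborn readmissions; sepsis 68, respiratory distress 21, endocrine/metabolic 2, trauma/injury 2. From Appendix C: 80 readmitted mothers and their diagnosis counts. From section 2.1: "3.6% of newborns were readmitted, 0.8% died, and 2.7% of mothers were readmitted". From section 4.4: 7,000 dyads. From section 4.9: expected loss below 5%.

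**Reproducing the printed figures.** 68/108 = 63.0%, 21/108 = 19.4%, 2/108 = 1.9%, 2/108 = 1.9%. All four match Table 8, so 108 is the denominator in use.

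**Readmissions without a listed diagnosis.**
- Minimum, with one diagnosis per newborn: 108 − (68 + 21 + 2 + 2) = 108 − 93 = 15, and 15/108 = 13.9%.
- Maximum, if every non-sepsis diagnosis was in a newborn who also had sepsis: 108 − 68 = 40, and 40/108 = 37.0%.

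**Is overlap plausible?** The maternal diagnoses sum to 41 + 34 + 15 + 4 + 2 + 2 + 1 + 1 + 1 + 1 + 1 + 8 = 111 for 80 mothers, so multiple answers were recorded there. The newborn follow-on items in Appendix A (still in hospital, number of nights) allow for one or more conditions. The 15 is therefore a lower bound.

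**Is an 'other' option used when offered?** Among mothers, 'Other' took 8/80 = 10.0% and 'Other Infection' 4/80 = 5.0%. The newborn item offers neither.

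**Projection to this study**, assuming one newborn per dyad and the prior readmission rate:

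| Loss | Readmitted newborns | No listed diagnosis, minimum (× 15/108) | Maximum (× 40/108) |
|---|---|---|---|
| 0% | 7,000 × 0.036 = 252 | 35 | 93 |
| 5% | 7,000 × 0.95 × 0.036 = 239 | 33 | 89 |

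Loss to follow-up hardly matters. At the prior cohort's own rate of incomplete follow-up, 1 − 2,926/3,236 = 9.6%, the figures are 228 readmitted and 32 without a listed diagnosis at the minimum.

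**The case against.** The strongest reply is that Appendix A is a list of variables, not the questionnaire. Some of its entries are plainly abbreviated: mode of delivery has no options, and one maternal symptom item has no list at all. Section 4.6.3 promises diagnoses during readmission without restriction, so the actual form may already hold the missing options. This stands in part: the gap is shown in the plan as written, not in the form. But Appendix A does print 'other' for the maternal diagnosis, discharge status and the baby's disposition, and it prints 'don't know' for newborn symptoms. The omission cannot simply be assumed to be shorthand.

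Appendix D is also an imperfect witness. It gives 26 deaths in Table 8 and 23 in Table 9, and its two percentages for care sought before death (61.5% and 43.5%) use different denominators (16/26 and 10/23). The readmission counts are not touched by this: 108 appears in both tables, and the four percentages reproduce on it.

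Several stronger readings are tempting, and the documents do not support them:
- **That the 15 had causes outside the list.** Table 8 does not say why they are unlisted. A row might even have been left out of the printed table.
- **That unlisted cases would be pushed into sepsis.** The item asks whether the family was told of each condition, which permits 'no' to all four. No misclassification is shown.
- **That yellow soles (10 of 131) reveals a missing diagnosis.** That count pools readmitted and dead newborns, is a symptom, and is not linked to the 15.
- **That these newborns would have no usable cause information.** Symptoms are collected as well.
- **That the choice of interventions would be distorted.** Section 4.7 ties the bundle to information from Phases II to IV, whereas causes of readmission are a Phase I outcome.

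**Conclusion.** The point holds as a small, well-evidenced improvement. The newborn item as written has no place for another diagnosis or for none conveyed. In the prior cohort, at least 15 of 108 readmissions (13.9%), and at most 40 (37.0%), have no listed diagnosis. In this study the lower bound corresponds to about 33 to 35 of 239 to 252 readmitted newborns. That rests on the prior readmission rate and the prior unlisted share carrying over, one newborn per dyad, 0 to 5% loss, and the form matching Appendix A.

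The consequence is that secondary outcome 3 would be only partly answered for newborns, because the reason for the remainder could not be determined. It would not be unanswerable. A reader might also infer a threat to the prediction models, but there is none: Appendix A counts a newborn admission of one or more nights for any reason, so the primary outcome does not depend on this item.

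**What to change.** Add 'other (specify)' and 'not told/don't know' to the newborn readmission diagnosis item, and state that several answers may be selected. If the form already has these options, correct Appendix A to show them. In the analysis of secondary outcome 3, report the share of readmissions in each category on the full denominator of readmitted newborns, with other, not told and missing shown as separate rows, and say that categories may overlap.

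The cost is a few extra options in one REDCap field and a little free-text coding, for perhaps 33 to 35 newborns at the lower bound. No extra visits or staff are needed.

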Appendix B: Journey Mapping Variables

Table 10. Journey Mapping Data Collection

Time Period	Data Collection Tool	Variables
Admission	Admission Variables	Time of departure from home
		Mode of transport from home to hospital (e.g., personal vehicle, Boda Boda, Bus, other)
		Date of arrival at hospital
		Date of admission
		Time of admission
		Describe any barriers observed (e.g., long wait times, language barrier between mom and healthcare worker)
Discharge	Patient Interview Questionnaire	Are mom and baby being discharged together?
		Date and time of discharge
		Describe any barriers observed (e.g., language barrier between mom and healthcare worker)
		Did mom receive discharge education, if so, types of topics discussed?
		Was a referral made for postnatal follow-up care? If so, when and where?
		If mother died during hospitalization: 
 Date of death Who was the infant discharged to Did mom received discharge education prior to death?
		If child died during hospitalization - Date of death
72-hour post-discharge	Maternal and Newborn Follow-up Telephone Interview	Travel time from hospital to home
		Mode of transport from hospital to home
		Did the time of discharged affect trip home?
		Barriers encountered on journey home
		Patient experience measures (Likert scales – e.g., felt healthcare worker spent enough time preparing them for discharge, were things explained in a way that was easy to understand, quality of discharge experience, etc.)
		Travel time from hospital to home
6 weeks post-discharge	Maternal and Newborn Follow-up and Telephone Interview	If postnatal care was sought, what motivated you to attend a follow-up visit?
		If referred but did not attend a follow-up, why not?

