2.3 Conceptual framework

Our conceptual framework is clearly embodied within the concept of precision public health. Ensuring all mothers receive the recommended 3 postnatal care (PNC) visits following a facility delivery is challenging from a resource perspective. The majority of mothers survive beyond the critical first 6 weeks. However, a proportion of dyads remain vulnerable during this period. Health systems, particularly those in resource limited settings, must be able to ensure those most in need of care can appropriately receive such care. As such, our work is guided by improving our ability to identify these vulnerable dyads and then developing a scalable and sustainable approach to ensuring the intensity of care is linked to the degree of risk.

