4.4 Study Population

Phase I: Observational Cohort Study

We will recruit 7,000 mother and newborn dyads from the two participating hospitals. Based on previously observed outcome and loss to follow-up rates, we will be able to measure the prevalence of maternal and newborn hospital readmission or death within a margin of error of 1% and develop prediction models with up to 30 candidate predictors for both maternal and newborn outcomes separately with this sample size.

Inclusion:

- Women and adolescent girls aged 12 and above delivering a single or multiple babies at the study hospital during the active recruitment phase.

Exclusion:

- Inability, for whatever reason, to provide informed consent.
- Language barrier
- Mother is from a refugee camp
- Mother has no access to phone or other means for follow-up
- Mother lives outside of hospital catchment area

We will continue to follow-up with all patients enrolled in the study. This includes enrolled mothers whose baby dies after discharge as well as enrolled babies whose mothers die. In the event that the mother dies, we will follow-up with the caregiver of the baby.

Table 3. Phase I sample size

Participants:	Sample size (n=7,000)
Maternal Infant Dyads	3,500 per facility (n=7,000)

Phase II: Patient Journey Mapping

We will randomly select 100 mothers (50 per facility) from the phase I cohort of 7,000 dyads to participate in journey mapping due to intense time to capture.

Inclusion:

- Women and adolescent girls aged 12 and above delivering a single or multiple babies at the study hospital during the active recruitment phase.
- Enrolled in Phase 1.

Exclusion:

- Inability, for whatever reason, to provide informed consent.

Exclusion:

- Inability, for whatever reason, to provide informed consent.
- Language barrier
- Mother is from a refugee camp
- Mother has no access to phone or other means for follow-up
- Mother lives outside of hospital catchment area

Table 4. Phase II sample size

Participants:	Sample size (n=100)
Maternal Infant Dyads	50 per facility (n=100)

Phase III: Process Mapping

We will purposively select a sample of 6 healthcare providers and 2 hospital administrators from each of the 2 study sites for participation in a process mapping exercise based on their level of experience, availability, and consultations from site leads (Table 4).

Inclusion:

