4.7 Study Outputs

Phase I: A pair of internally validated prediction models (one each for mom and baby) for identifying dyads at high-risk of death or hospital readmission after discharge following live birth in-hospital. Our candidate predictors for our models will be maternal and infant characteristics collected at the time of admission and discharge following a facility delivery.

Phase II-IV: A descriptive account of all aspects of the discharge process and postnatal care follow-up visits for facility-based deliveries, including identification of barriers and solutions to effective postnatal care from the perspective of patients, caregivers, and facility staff. We will use this information to inform the development of a bundle of interventions, with separate components for high-risk mothers and high-risk newborns, and a locally supported and culturally safe strategy for implementing this bundle of interventions.

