Qualitative Analysis: We will analyze data collected descriptively and report summary statistics. We will develop a diagram of the discharge process, identifying key areas for improvement during the peri-discharge and post-discharge process¹¹. We will analyze FGDs using a framework method, which allows themes to be developed inductively from participants and deductively from existing literature¹². Through an iterative process, transcripts will be coded and analyzed for descriptive and interpretive themes using NVivo. Descriptive themes include barriers to care and post-discharge health-seeking behavior, while interpretive themes focus on caregiver perspectives of maternal and neonatal death and the role of the health system. We will generate frequencies to describe reported medical symptoms, health-seeking behavior, and barriers to care, and summarize common themes. We will use member checking to improve the validity of our results, creating a summary document of the main findings that will be reviewed by health workers who participated in the focus groups. Feedback from patients and families will be obtained over telephone with research nurses who will explain the main findings verbally.

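### The journey-mapping interview asks why postnatal care was missed only of mothers who had been referred, so unreferred non-attenders and, on the plain reading, partial attenders give no individual reason

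*Combined protocol and SAP*

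**What the plan says.** Phase II takes a random subset of the cohort (section 4.4): "We will randomly select 100 mothers (50 per facility) from the phase I cohort of 7,000 dyads to participate in journey mapping". According to section 4.6.3, these mothers get extra questions on their "perspectives on the current system of post-natal care, and post-discharge pathways, at various time periods", the last of them at the six-week telephone interview.

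Appendix B, Table 10, lists the extra items. Three matter here:

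- At discharge: "Was a referral made for postnatal follow-up care? If so, when and where".
- At six weeks, for those who sought care: "If postnatal care was sought, what motivated you to attend a follow-up visit". There is no referral condition.
- At six weeks, for those who did not: "If referred but did not attend a follow-up, why not". Here referral is a condition.

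The Quantitative Analysis paragraph of section 4.10 says that the journey-mapping survey and interview variables will each be summarised by frequency and distribution. Section 4.7 promises, for Phases II to IV together, "identification of barriers and solutions to effective postnatal care from the perspective of patients".

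**The concern.** The two six-week items are not symmetrical. A mother who attended without a referral is asked what brought her. A mother who stayed away without a referral is not asked what kept her away. Because the discharge form records whether a referral was made, the plan allows for mothers who have none.

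The second gap concerns partial attendance. Section 2.3 sets the standard at several visits: "Ensuring all mothers receive the recommended 3 postnatal care (PNC) visits following a facility delivery is challenging". A mother who went once and stopped has attended a follow-up, so on the plain reading she gets the motive question and not the reason question.

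What is at stake is the content of one Aim 2 variable. Reasons specific to unreferred mothers, such as not knowing that a visit was expected, and reasons for stopping after the first visit would be missing from the only individual-level item designed to collect reasons. The tabulated answers could be taken as reasons for missed postnatal care in general when they describe a narrower group.

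**Working it through.** **1. Is there another individual-level item on reasons?** The listed variables, side by side:

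| Source | What it records | Reason for missed postnatal visits? |
|---|---|---|
| Appendix A, six-week maternal and neonatal items (all 7,000 dyads) | Care seeking, number and timing of visits, illness, readmission | No |
| Appendix A and B, 72-hour call | Travel, barriers on the trip home, experience of discharge | No |
| Appendix B, admission and discharge | Barriers observed in hospital, discharge education, referral | No |
| Appendix B, six weeks | Motive (attenders); reason (referred non-attenders) | Only if referred |

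The filtered item is the only one.

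**2. The plan's own figures.** Phase II: 50 × 2 = 100. Focus groups: 12 × 4 × 2 = 96. Both reproduce. Section 4.4 justifies the 100 by the time that data capture takes, not by a precision calculation.

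**3. How many mothers would be asked?** Expected number asked = 100 × P(no visit) × P(referred, given no visit). Inputs:

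- P(no visit), higher value: Chapter One gives 57% of women nationally with one skilled-provider visit within 41 days. Reading the remainder as none gives 1 − 0.57 = 0.43.
- P(no visit), lower value: Appendix C, Table 7, gives 4/80 = 0.05, in readmitted mothers only.
- P(referred, given no visit): not in the documents. Assumed range 25% to 100%.

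The worst-case 95% half-width for a proportion is 1.96 × √(0.25/n).

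| Referred (assumed) | Asked, 43% no visit | Non-attenders not asked | Half-width, points | Asked, 5% no visit |
|---|---|---|---|---|
| 100% | 43 | 0 | ±15 | 5 |
| 75% | 32 | 11 | ±17 | 3.8 |
| 50% | 21.5 | 21.5 | ±21 | 2.5 |
| 25% | 11 | 32 | ±30 | 1.2 |

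No half-width is shown for the last column because the normal approximation is unreliable at about 5 or fewer. Section 4.9 expects less than 5% loss to follow-up; a 5% loss would multiply each count by 0.95.

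**4. Partial attenders.** In Table 7, (33 + 32)/80 = 65/80 = 81% made one or two visits, and (4 + 33 + 32)/80 = 69/80 = 86% made fewer than three. This gap does not depend on the referral rate.

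**5. After the change.** With the question put to every mother with no visit, about 43 of 100 are asked on the national figure (±15 points) or about 5 on Table 7. With fewer than three visits as the criterion, about 86 are asked on Table 7 (±10.6 points), or 95 × 0.8625 = 82 after a 5% loss (±10.8 points).

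**The case against.** The best case for the plan has five parts.

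*The barrier frequencies come from elsewhere.* A reader might infer that all the barrier frequencies promised for Aim 2 rest on this small group. The documents do not support that. The sentence "We will generate frequencies to describe reported medical symptoms, health-seeking behavior, and barriers to care" stands in the Qualitative Analysis paragraph of section 4.10, after the coding of focus-group transcripts, and names neither instrument nor denominator. What the filter does limit is the separate summary of the journey-mapping variable.

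*The focus groups cover barriers.* They do: 96 participants, 48 of them mothers, with no referral filter (sections 4.4 and 4.6.3). It would therefore be wrong to say that unreferred or partially attending mothers are never asked about barriers, or that the intervention bundle would be built on this one item; section 4.7 draws on Phases II to IV together. Still, section 4.5 describes purposive selection from a convenience sample, and a group discussion does not tie a reason to a mother's referral status or visit count. The random sample is in Phase II.

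*Appendix B is a variable list, and the telephone guides are semi-structured (section 4.6.2).* Interviewers may probe, and the wording about not attending a follow-up could cover one missed visit among several. That is why the point about partial attenders holds only on the plain reading. Optional probing gives no defined denominator.

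*The skip may be deliberate.* For an unreferred mother, the lack of referral is already recorded and can be cross-tabulated with attendance. But that does not show that it was her reason; cost or distance may have mattered more. The motive item itself allows for attendance without referral.

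*The figures are weak.* The 43% is national, and section 2.2 puts home births at 26.6%, whereas this cohort delivers in two referral hospitals. Table 7 covers 80 readmitted mothers. If only 5% make no visit, the numbers are small because few mothers stay away altogether; lifting the referral condition alone raises the count only to about 5. All of this stands, so the figures are illustrations.

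**Conclusion.** The point holds in limited form. As listed, the only individual-level item on why postnatal care was missed is conditional on referral, while the matching item for attenders is not. Its descriptive statistics would describe referred non-attenders, and no other listed individual-level item collects the reason from unreferred non-attenders or, on the plain reading, from mothers who made fewer visits than recommended.

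The size cannot be fixed from the documents. On the national figure and an assumed referral rate of 25% to 100%, between 32 and 0 of about 43 complete non-attenders go unasked; if every mother is referred, none of them is lost. The loss of partial attenders remains at any referral rate and could be the larger one (81% in Table 7, indicative only).

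This is a cheap improvement to one descriptive Aim 2 variable. Aim 1, the primary outcome and the prediction models are not affected.

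**What to change.** In Table 10, remove the referral condition. Ask every Phase II mother who made no postnatal visit, or fewer than the recommended number, a neutral open question, for example: *Why did you not attend any, or any further, postnatal visits?* Neutral wording matters because a mother may simply have felt well or not known of the visit; asking what prevented her would presuppose an obstacle.

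State the recommended number once and use it as the criterion. The Abstract gives at least four visits, while Chapter One and section 2.3 give three, and these need to be reconciled before the item is programmed.

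Keep referral status as the discharge variable already listed, and tabulate the reasons by referral status and by number of visits made.

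The cost is the rewording of one telephone item and one or two extra minutes in at most 100 calls. Reasons not collected at the six-week call cannot be rebuilt from the other listed variables.
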